**Figure 1. Geographic Location of the TEAMS Clinical Partners (clinics= 43)**

## **Enhancement Study**

For the Enhancement study, participants received all testing through a teleassessment platform, followed by 20 synchronous telerehabilitation sessions in line with our original study design for the other two arms (TeleCAM, DirectCAM). A total of 8 physical therapists were involved in the testing and rDirectCAM delivery of the Enhancement study.

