## Sample Size Calculations and Study Power

For the Main study an *a priori* power analysis was conducted based on sample size estimation for longitudinal designs with attrition with at least 30 sites. Based on the conservative power and sample size calculations, the project was powered for a minimum of 533 participants completing the study with an assumption of a 35% attrition rate; therefore, a total estimated sample size of 820 was needed to detect a between group effect. We assumed intent to treat analyses, 80% power, two-sided family-wise error rate of 0.05, intra-class correlation of 0.05, and a correlation of 0.3 among repeated measures. We also assumed an attrition rate of 35% and a small minimally detectable effect size of 0.2. We make a conservative assumption that the correlation between repeated measures would be 0.3. We have four primary and four secondary outcomes and hence the sample size was estimated after accounting for multiple testing and with a type 1 error rate of 0.00625 for each hypothesis test.

[figure not shown]
For the Enhancement study, we assumed ANCOVA with a pre-post correlation of 0.7, 80% power, one-sided test with statistical significance of 0.05, and attrition rate of 25%. Further, these sample size calculations assumed a non-inferiority margin of -4 units for MFIS, where fatigue is one our key primary outcome identified by the stakeholders in our project. A change of 4 or greater has been found clinically meaningful for quality of life. Based on these assumptions a sample size of 55 completers in rDirectCAM were needed and with an attrition

rate of 25%, we needed 74 participants in rDirectCAM.

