## Analytical and Statistical Approaches

### **Main Study**

Our analysis was following ITT protocol as all participants assigned to the randomized clinics and completed baseline assessment were included in the analysis.

Our primary hypotheses were about comparing the change in the 11 outcomes (listed in **Table 4**) between baseline and 12th month follow-up across the two arms. We considered these 11 hypothesis tests for the 11 outcome variables as part of a single family of hypotheses. We employed the Holm-Bonferroni method for controlling the overall family wise error rate and computed adjusted *p*-values. For each outcome we used a linear mixed effects model, with TeleCAM arm as the reference category, and accounting for the correlated nature of the data due to the nesting of participants within a clinic as random effects. Crude models included fixed effects included both Arms (TeleCAM, DirectCAM), Time (baseline [reference], 3 month, 6 month, 12 month), an Arms X Time interaction, and accounted for randomization strata (clinic location being urban vs. non-urban). The interaction of Arms and Time variables was the primary effect of interest since it quantified the differences within Arm change in the outcome from baseline over time of the two Arms. For example, based on the fitted model that included the interaction between Arm and Time, the difference in change over time from baseline to 12 months between DirectCAM and TeleCAM were estimated. Contrast statements were used to test the null hypotheses in conjunction with the fitted model coefficients and standardized differences in the average treatment effect reported. The estimates of the change in health and function outcomes for each arm and their 95% confidence interval were also reported. As a sensitivity analysis, similar models additionally adjusted for sex, race, and post-COVID data collection measure indicated were also ran. Note that, since post-COVID, data collection for patient reported outcomes was conducted remotely for remaining participants, the former was also included as a covariate in the adjusted model. Next, missingness in primary and secondary outcomes were addressed using multiple imputation technique (MCMC) via PROC MI in SAS,

assuming missing at random. Additional sensitivity analyses were conducted using wild bootstrap to assess the robustness to model assumptions.

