Our general analytic approach was to leverage the linear mixed modeling framework to account for repeated nature of data. Appropriate contrasts were applied using the fitted model. Sensitivity analyses were performed to assess distributional and other modeling assumptions. Missing data was imputed using multiple imputation where necessary. The non-inferiority ( $-\Delta$ ) of the rDirectCAM was assessed by comparing the lower limit of confidence interval for each outcome to its corresponding margin so that if the lower bound was above this margin, then the rDirectCAM was deemed non-inferior. For the MFIS and TUG assessments, wherein an elevated score signified a deterioration in the outcome, we juxtaposed the upper limit of the

confidence interval against a predefined margin. Non-inferiority was deemed established when the upper bound was less than  $-\Delta^{133}$ .

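### The Enhancement analysis specifies no clinic or therapist clustering, so its confidence limits are too narrow if outcomes cluster in change from baseline

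*Combined protocol and SAP*

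**What the plan says.** Under Analytical and Statistical Approaches, the Enhancement Study text gives the model as follows: "Our general analytic approach was to leverage the linear mixed modeling framework to account for repeated nature of data". It continues: "Appropriate contrasts were applied using the fitted model", and "Sensitivity analyses were performed to assess distributional and other modeling assumptions". It also describes stabilized inverse-probability weighting to balance rDirectCAM against DirectCAM, and multiple imputation. Repeated measurement is the only source of correlation it mentions. Non-inferiority is decided by comparing one limit of a 95% confidence interval with a margin.

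For the Enhancement study, Sample Size Calculations and Study Power lists ANCOVA with a pre-post correlation of 0.7, 80% power, a one-sided 0.05 test, 25% attrition and a 4-unit MFIS margin. It lists no ICC and no design effect.

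The Main study is handled differently. Its sample size assumes "intra-class correlation of 0.05, and a correlation of 0.3 among repeated measures", and its model is described as "accounting for the correlated nature of the data due to the nesting of participants within a clinic as random effects". On delivery of the remote arm, Study Setting states: "A total of 8 physical therapists were involved in the testing and rDirectCAM delivery of the Enhancement study".

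**The concern.** The DirectCAM comparators were treated within clinics, and the plan treats that nesting as real when it compares them with TeleCAM. The nesting does not disappear when the same arm is compared with rDirectCAM. The remote arm has clusters of its own: with no more than 8 therapists delivering, each treats on average about 7 or more of the 55 planned completers.

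A non-inferiority conclusion rests on a single confidence limit. If positive clustering in the contrast is left out, that limit moves inward, which is the anti-conservative direction. The weights do not repair this: they address imbalance between arms, not correlation between participants who share a therapist or clinic.

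**Working it through.** **The plan's own figures.** The inflation for attrition reproduces: 55 / 0.75 = 73.3, rounded up to 74. The 55 can be neither confirmed nor refuted, because neither the MFIS standard deviation (SD) nor the number of DirectCAM comparators is stated. With one-sided 0.05, 80% power, no true difference and no design effect, the standard error (SE) must be 4 / (1.645 + 0.842) = 1.61. Setting SD × √(1 − 0.7²) × √(1/55 + 1/n₀) equal to 1.61 gives a raw SD of about 11.8 with n₀ = 55, or about 15.2 with n₀ = 266.

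**Inputs.**
- rDirectCAM: 55 completers (Sample Size Calculations) over 8 therapists (Study Setting), so 55/8 = 6.875 each. The 8 covers testing and delivery together, so it is an upper limit on those delivering.
- DirectCAM: the number is not stated. Assumed range 55 (equal to rDirectCAM) to 266 (about half of the 533 Main-study completers).
- DirectCAM clinics: about 20 assumed, half of the 40 randomized. Cluster sizes are then 2.75 to 13.3, taken as equal.
- ICC: 0.05, the Main-study planning value, assumed here to apply to change; varied from 0.01 to 0.10.

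**Design effect (DE)**, 1 + (m − 1) × ICC, at ICC 0.05:
- rDirectCAM: 1 + 5.875 × 0.05 = 1.294
- DirectCAM, 55 comparators: 1 + 1.75 × 0.05 = 1.088
- DirectCAM, 266 comparators: 1 + 12.3 × 0.05 = 1.615

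**SE ratio**, √[(DE₁/n₁ + DE₀/n₀) / (1/n₁ + 1/n₀)]:
- 55 comparators: √[(1.294 + 1.088)/2] = 1.091
- 266 comparators: √[(1.294/55 + 1.615/266) / (1/55 + 1/266)] = √(0.02959/0.02194) = 1.161

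The unclustered interval is therefore 8% to 14% too narrow (1 − 1/1.091 and 1 − 1/1.161).

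**One-sided error with the true difference on the margin**, Φ(−z / SE ratio):

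| ICC for change | 95% interval rule (nominal 2.5%) | One-sided 0.05 test (nominal 5%) |
|---|---|---|
| 0.01 | 2.7% to 2.9% | 5.3% to 5.6% |
| 0.02 | 2.9% to 3.3% | 5.6% to 6.2% |
| 0.05 | 3.6% to 4.6% | 6.6% to 7.8% |
| 0.10 | 4.8% to 6.6% | 8.1% to 10.3% |

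In each cell the lower figure is for 55 comparators and the upper for 266.

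**Power with the correct SE at one-sided 0.05**, Φ(2.487 / SE ratio − 1.645), at ICC 0.05: Φ(0.634) = 74% with 55 comparators and Φ(0.496) = 69% with 266.

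**Simulation check**, 20,000 replicates of a change-from-baseline contrast analysed without clustering. With ICC 0.05 in change, error was 3.7% (55 comparators) and 4.4% (266) at nominal 2.5%, and 6.7% and 7.6% at nominal 5%. With ICC 0.05 only in a stable cluster level, equal at baseline and follow-up, error was 2.5% and 4.8% (266 comparators): no inflation.

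**The case against.** A reader might infer that clustering was deliberately left out and that the reported limits are therefore wrong. The documents do not support that. The model sentence is a summary that lists no random effects at all, so the text is silent rather than exclusive. What stands is that the only correlation structure specified is repeated measurement, and that the analysis run as written would not allow for clusters.

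The strongest objection concerns the contrast. The Main study defines its effect as a difference in change from baseline. If the Enhancement contrast is of that kind, a stable clinic or therapist level cancels, as the simulation shows. This is correct and makes the consequence conditional. It does not remove it, because differences between therapists in delivery act after baseline and so appear in change. Nor does the text say which contrast is used.

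The magnitude also rests on borrowed inputs. The ICC belongs to the clinic-randomized Main study, and the comparator number is unstated; hence the ranges. At ICC 0.01 the effect is small.

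The decision level matters too. The sample size uses one-sided 0.05, whereas one limit of a 95% interval is one-sided 0.025. At ICC 0.05 the error under the interval rule stays below 5%, the level used in planning.

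Finally, it is tempting to say that non-inferiority is declared too often for every outcome. For MFIS and TUG the plan requires the upper limit to be below −Δ. Read with Δ = 4 for MFIS, this demands superiority by 4 units, so the error rates above do not describe the rule as written. They apply to outcomes judged on the lower limit, such as BBS, grip strength and the SF-36 scales.

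**Conclusion.** The point holds in conditional form. The Enhancement analysis specifies no clinic or therapist clustering, although the plan recognises clinic clustering for the same comparator arm and the remote arm rests on very few therapists. If outcomes cluster in change, the limits as specified are too narrow. At ICC 0.05 the inflation is moderate: about 1 to 2 percentage points above the nominal 2.5% under the interval rule. Over ICC 0.01 to 0.10 the error runs from 2.7% to 6.6%, and it is 2.5% if only a stable level is clustered.

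These sizes depend on the assumed comparator number, clinic count and equal cluster sizes, and on carrying the Main-study ICC over to change. This is more than a missing detail, because the deciding limit depends on it and a better method is cheap. It does not show that any non-inferiority conclusion is false.

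**What to change.** State the cluster structure of the Enhancement analysis: clinic in DirectCAM, treating therapist in rDirectCAM. Use a cluster-robust or cluster-bootstrap variance together with the inverse-probability weights, or add a cluster-by-time random effect. A random intercept alone is not enough, because it would barely alter the interval for a change contrast. Apply a small-sample correction, since there are only about 8 therapist clusters, and report the estimated ICC. If clustering was already handled, say how.

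State the contrast, and restate the Enhancement power with the ICC of 0.05. Reconcile the upper-limit rule for MFIS and TUG before quoting an error rate for them, and reconcile the one-sided 0.05 of the sample size with the 95% interval of the analysis.

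The cost is a change to the variance estimation or one model term, a re-run and a few sentences of text. The downside is somewhat wider intervals and a less favourable stated power.

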### **Enhancement Study**

We used a quasi-experimental design to compare rDirectCAM with DirectCAM. Our hypothesis posits that the observed difference in outcome effects between rDirectCAM and DirectCAM is less than a predetermined non-inferiority margin ( $-\Delta$ ). These margins were selected based on the MCID or minimal detectable change (MCD) of the studied outcomes among MS population published in literature (MFIS= 4, BBS= 3, TUG= 10.6, FTSTS= 13, Grip-strength= 10.5, SF-36 Physical functioning= 7.1 and SF-36 pain= 4.9).

Specifically, we hypothesized that the effect of rDirectCAM was not inferior to that of DirectCAM by a margin that was considered clinically acceptable, thereby affirming the non-inferiority of rDirectCAM in comparison to DirectCAM. In other words, if the resulting *p*-value was significant, this would mean that we rejected the null hypothesis which stated that the difference in the effect between two arms were more than the non-inferiority margin. Statistical significance level of 0.05 and at confidence interval 95%, same as superiority trials,

was applied to determine non-inferiority. To achieve a balance between the study arms, several analyses involved regression-based parametric adjustment measures that are sensitive to model misspecification. Propensity scores are another widely used measure to achieve balance or matching between the study arms. These scores model the probability of being assigned to the given treatment conditional on observed baseline covariates obtained via measures including matching, inverse probability treatment weighting (IPTW), and stratification and covariate adjustment. Matching-based measures such as nearest neighbor matching algorithm often led to study participants being excluded when a match was not available. This may have potentially biased the effect estimates. When this occurred, we utilized stabilized IPTW, a non-parametric balancing strategy, to achieve balance between the two study arms (rDirectCAM and DirectCAM). Using this weighted analysis, we modeled the causal parameter as the inverse of the conditional probability of receiving the treatment given the observed covariates, a technique that provides asymptotically unbiased estimates and uses data on all available study participants across the two arms.

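### The printed non-inferiority rule for MFIS and TUG (upper limit below −Δ) is not a non-inferiority test, FTSTS is left out of the upper-limit exception, and the contrast direction is not stated

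*Combined protocol and SAP*

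**What the plan says.** All of this is in the Combined protocol and SAP, mostly in the Enhancement Study part of Analytical and Statistical Approaches.

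- **Hypothesis.** The study posits that "the observed difference in outcome effects between rDirectCAM and DirectCAM is less than a predetermined non-inferiority margin", written −Δ. The margins are then listed as positive values: MFIS 4, BBS 3, TUG 10.6, FTSTS 13, grip strength 10.5, SF-36 physical functioning 7.1, SF-36 pain 4.9. A significant p-value means "we rejected the null hypothesis which stated that the difference in the effect between two arms were more than the non-inferiority margin".
- **Default rule.** Non-inferiority is judged by "comparing the lower limit of confidence interval for each outcome to its corresponding margin"; a lower limit above the margin passes.
- **Exception.** "For the MFIS and TUG assessments, wherein an elevated score signified a deterioration in the outcome", the upper limit is used instead: "Non-inferiority was deemed established when the upper bound was less than" −Δ.
- **Contrast.** The text says only "Appropriate contrasts were applied using the fitted model". No subtraction order or coding of change is given for this comparison.
- **Level.** "Statistical significance level of 0.05 and at confidence interval 95%, same as superiority trials".
- **Sample size section.** For the Enhancement study, "these sample size calculations assumed a non-inferiority margin of -4 units for MFIS", with a one-sided 0.05 test and 80% power.
- **Study Outcomes.** FTSTS is the time taken for five sit-to-stand transfers, so a higher value is worse. It was collected in the Enhancement study.

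**The concern.** For an outcome where higher is worse, a non-inferiority test on new minus reference asks whether the upper limit stays below +Δ. The printed rule puts the threshold at −Δ, on the other side of zero. It affects MFIS, the outcome on which the Enhancement study was sized.

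The stated reason for the exception, that a higher score means deterioration, applies equally to FTSTS, but FTSTS is not named. It therefore falls under the lower-limit rule.

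On rDirectCAM minus DirectCAM, the two errors run in opposite directions. MFIS and TUG are held to too strict a standard, so the risk is a false failure to show non-inferiority. FTSTS is held to too lenient a standard, so the risk is a false claim of non-inferiority. Without the contrast direction, a reader cannot work out the intended rule or check a reported conclusion against it.

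**Working it through.** **Step 1: sign algebra for MFIS and TUG, Δ > 0, raw scores (higher is worse).**

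- rDirectCAM − DirectCAM: an upper limit below −Δ shows rDirectCAM better by more than Δ. This is superiority by a margin.
- DirectCAM − rDirectCAM: an upper limit below −Δ shows rDirectCAM worse by more than Δ. This is inferiority.

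Scoring change as improvement only flips the sign and leads back to one of these two cases.

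**Step 2: can any single coding rescue the whole rule?** Seven outcomes have margins. Taking the margin literally as −Δ:

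| Coding | Outcomes with a correct rule |
|---|---|
| rDirectCAM − DirectCAM, Δ > 0 | 4 (BBS, grip strength, two SF-36 scales) |
| DirectCAM − rDirectCAM, Δ > 0 | 1 (FTSTS) |
| rDirectCAM − DirectCAM, Δ < 0 | 2 (MFIS, TUG) |
| DirectCAM − rDirectCAM, Δ < 0 | 0 |
| Change scored as improvement, rDirectCAM − DirectCAM, Δ > 0 | 5 (all but MFIS, TUG) |

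None gives 7.

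**Step 3: the plan's own figure.** Inflating 55 completers for 25% attrition gives 55/0.75 = 73.3, rounded up to 74, as stated. The 55 cannot be reproduced because neither the MFIS standard deviation nor the comparator size is given. The standard error can be back-solved without them.

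**Step 4: size of the MFIS error.** Inputs from the sample size section: margin 4, one-sided 0.05, 80% power. Assumption: true difference 0.

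SE = 4/(1.645 + 0.842) = 1.609.

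With the 95% interval of the analysis section, on rDirectCAM − DirectCAM:

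- Printed rule: P(upper < −4) = Φ(−4/1.609 − 1.960) = Φ(−4.446) = 4.4 × 10⁻⁶.
- Conventional rule: P(upper < +4) = Φ(4/1.609 − 1.960) = Φ(0.527) = 0.70.

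With a 90% interval, which matches one-sided 0.05, the figures are 1.8 × 10⁻⁵ and 0.80.

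Range over assumed standard errors (95% interval, true difference 0):

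| SE | P(upper < −4) | P(upper < +4) |
|---|---|---|
| 1.2 | 6.0 × 10⁻⁸ | 0.92 |
| 2.0 | 3.7 × 10⁻⁵ | 0.52 |
| 2.5 | 1.9 × 10⁻⁴ | 0.36 |

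If planning had assumed a true difference of +1 or −1, the implied SE is (4 ∓ 1)/2.486, that is 1.21 or 2.01. The printed rule then passes with probability 5 × 10⁻¹⁰ or 2.8 × 10⁻⁴, against 0.70 for +4 in both cases.

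On the reverse contrast (95% interval, SE 1.609), an rDirectCAM truly worse by 6, 8.5 or 10 points passes the printed rule with probability 0.24, 0.80 or 0.96. For 8.5: Φ((8.5 − 4)/1.609 − 1.960) = Φ(0.837) = 0.80.

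**Step 5: size of the FTSTS error.** On rDirectCAM − DirectCAM, take a true slowing equal to the margin, 13 (the unit is not printed). The default rule passes with probability Φ((13 + 13)/SE − 1.960). The standard errors are assumed:

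| SE | P(lower > −13) |
|---|---|
| 4 | 0.999997 |
| 6 | 0.991 |
| 8 | 0.901 |

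The rule upper < +13 would pass with probability Φ(−1.960) = 0.025 at that point.

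**The case against.** The best defence is that −Δ is a loose label for the margin. The section attaches it to positive values, and it introduces the upper-limit comparison as one against a predefined margin. The right tail is chosen for MFIS and TUG, for the right reason, and the null is conventional. The direction can also be inferred: on raw scores, a lower limit for higher-is-better outcomes and an upper limit for higher-is-worse outcomes fit only rDirectCAM minus DirectCAM. On that reading six of the seven outcomes have a correct rule, and the MFIS and TUG problem is one wrong sign. Even taken literally in that direction, the sign error is conservative and cannot create a false non-inferiority claim for those two outcomes.

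Much of this stands. A notation slip is plausible, the pass rate of 4 in a million may belong to a rule that was never run, and the reverse-contrast figures describe the less likely order. The FTSTS figures rest on assumed standard errors and an extreme scenario, and the FTSTS conclusion is unchanged if both limits lie within ±13.

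The defence still leaves FTSTS wrong, because a sign correction does not add a missing outcome. FTSTS may have been dropped from the list by oversight, but it is the error that could produce a false claim. The direction has to be inferred from the very sentences that conflict.

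**Conclusion.** The point holds. As printed, the MFIS and TUG criterion contradicts the section's own null and is not a non-inferiority test under either subtraction order with Δ > 0. FTSTS is wrongly left out of the exception on the direction that suits BBS, grip strength and SF-36. No reading, including the label reading, gives a correct rule for all seven outcomes.

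If the printed rule was applied on rDirectCAM minus DirectCAM, non-inferiority on MFIS was practically unattainable for equal arms, and a full-margin slowing on FTSTS would pass at least 90% of the time for the assumed standard errors of 4 to 8. These sizes rest on a normal approximation; the MFIS figures also assume a true difference of 0 and the back-solved standard error.

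Confidence is high that the text is wrong. Whether any conclusion is affected is unknown, because the document contains neither code nor results for this comparison. The Main study analysis is not affected. This must be corrected because it is the decision threshold for the outcome that sized the Enhancement study.

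**What to change.** 1. State the contrast as rDirectCAM minus DirectCAM on raw scores, with Δ > 0.
2. Declare non-inferiority for MFIS, TUG and FTSTS when the upper limit is below +Δ, and for BBS, grip strength and the two SF-36 scales when the lower limit is above −Δ.
3. Make the sign of the MFIS margin in the sample size section agree with that coding. The value −4 is not an error in itself; it would fit a coding in which positive change means improvement.
4. Confirm from the code which rule was applied. If it was the conventional one for all three higher-is-worse outcomes, only the text changes. If the printed rule was used, re-read and re-report the MFIS, TUG and FTSTS conclusions from the existing confidence limits.

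The cost is a few lines of SAP wording and a code check, and at most a re-reading of limits already computed. No new data are needed.
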